Specific Aim 1 (Primary Aim): To determine the effectiveness of ZNS treatment in reducing drinking on the primary outcome measure: drinks per week (measured using the Timeline Followback Method), for eight weeks at a target dose of 600 mg of ZNS daily for 160 heavy-drinking, alcohol-dependent veterans. We hypothesize that ZNS treatment will reduce the heavy drinking days per week and the total drinks per week significantly more than the placebo and that the benefits will persist at three months follow-up after treatment.

Specific Aim # 2 (Secondary Aim): To examine the effects of ZNS treatment on heavy drinking days per week, , percentage of subjects with no heavy drinking days (PSNHDD) the urge to drink (craving), biomarkers of alcohol intake, clinical global impression, medication tolerability, and other patient-centered outcomes. We hypothesize that ZNS will demonstrate significantly greater improvements than the placebo on these measures by the treatment endpoint as well as at follow-up.

Specific Aim #3 (Secondary): To use telephone-based daily process data collection to elucidate the mechanism of action of ZNS as it relates to changes in craving, anxiety, and genetic variation. *This method has been shown to elucidate the mechanism of action of topiramate, as well as its pharmacogenetic interactions.* We hypothesize that ZNS' effects will be moderated by genetic variation, craving, and anxiety, but mediated through changes in self-efficacy to reduce heavy drinking.

Specific Aim #4 (Exploratory): The exploratory aim is to examine the pharmacogenetic interactions between ZNS and the therapeutic response. We hypothesize that both the long (L) allele of the VNTR polymorphism in exon 3 of the *DRD4* gene and the CC genotype of the *DBH* rs1611115 (C-1021T) SNP will show a pharmacogenetic effect with ZNS, as evidenced by a greater reduction in drinking than for the short (S) allele and T carriers respectively.

Specific Aim #5 (Exploratory) To compare ZNS and placebo-treated subjects on pre- and post-treatment changes in measures of stress-reactivity (i.e., stress-induced anxiety, alcohol craving, autonomic nervous system activity), cue-elicited craving, and impulsivity. We hypothesize that ZNS will attenuate stress-reactivity, cue-elicited craving, and impulsivity more than placebo in a stress laboratory paradigm, and that attenuation of those measures will be associated with reduction in drinking.

4. BACKGROUND:

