Impulsivity will be assessed through the Balloon Analogue Risk Task (BART) (70) and Barrett Impulsivity Scale (BIS) (71). The Go/No-Go Task will assess the ability to withhold responses to an infrequently occurring target (No-Go trials). A series of blue and green rectangular shapes are presented every 1150 ms and participants are instructed to press a spacebar every time the green rectangular shape appeared, and to give equal importance to speed and accuracy. The primary outcome is the number of errors on the No-Go trials (97, 98).

State-Trait Anxiety Inventory (STAI) will be used to assess anxiety symptoms; the full version will be used at the start of the lab session and the shorter version (STAI-6) will be used for all other indicated timepoints (75).

6.H.7. Physiological Measures: BP and HR will be assessed using an SD-700 monitor.

6.I. Statistical Plan and Power Analysis:

6.I.1. Procedures: Procedures for the monitoring and analysis of data were developed during previous clinical trials conducted in the VAARC and CTNA and will be overseen by [name].

6.I.2. To Examine The Effectiveness Of ZNS (Specific Aim 1, Primary Outcome):

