We will use the percentage of subjects with no heavy drinking days (**PSNHDD**) as the primary outcome variable. This outcome is the FDA recommended endpoint for pivotal trials, and is described in Falk et al., (2010). The PSNHDD can be derived from each subject's TLFB data. An important initial consideration in considering effectiveness will be to identify baseline differences between groups that may have occurred despite randomization. **Successful outcomes during the treatment trial will be defined in terms of a statistically significant difference on the primary outcome measure: PSNHDD, compared during the 8 weeks of active treatment at the target dose, allowing for a 6 week grace period for the medication titration.** For all analyses, heavy drinking days will be defined as follows; for men > 5 drinks in a day and for women > 4 drinks in a day. Patients will be followed irrespective of whether they continue to receive medication treatment, so that analysis will include all data available for the 8-week treatment period. The analysis will be **intent-to-treat**, and dropouts will be considered as having relapsed to heavy drinking. We will use a logistic regression analysis with PSNHDD as a categorical dependent variable. Medication condition (placebo or ZNS) will be the main independent variable, and we will include the variables of early onset of alcoholism (EOA, binary), and the use of additional psychotropics (e.g., antidepressants, a binary variable) as covariates. The α will be set at .05 for the primary outcome variable. Between site differences will be explored.

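### The aims name drinks per week as the primary outcome, but the statistical section makes it a secondary and gives the primary place and the .05 to PSNHDD

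*Combined protocol and SAP*

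**What the plan says.** Section 3, Specific Aim 1 (Primary Aim), sets out to test zonisamide for "reducing drinking on the primary outcome measure: drinks per week (measured using the Timeline Followback Method". Its hypothesis does not mention PSNHDD: "We hypothesize that ZNS treatment will reduce the heavy drinking days per week and the total drinks per week significantly more than the placebo". Specific Aim 2, labelled secondary, includes "percentage of subjects with no heavy drinking days (PSNHDD) the urge to drink (craving" among its outcomes.

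Section 6.I.2 carries the heading "To Examine The Effectiveness Of ZNS (Specific Aim 1, Primary Outcome", so it presents itself as the analysis of that same aim. It takes PSNHDD "as the primary outcome variable. This outcome is the FDA recommended endpoint for pivotal trials". Success is "defined in terms of a statistically significant difference on the primary outcome measure: PSNHDD", and alpha "will be set at .05 for the primary outcome variable". Later in 6.I.2, drinks per week and heavy drinking days per week appear as secondary outcomes under Aim 2, with a Bonferroni correction. Significance on secondary measures of both heavy drinking and drinking, with effects of clinically significant size, counts only as a relative success.

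Section 6.I.6 gives its primary power statement to PSNHDD and treats total drinks per week as secondary.

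**The concern.** Two parts of one document use the term primary outcome for Specific Aim 1 and attach it to different variables. No sentence makes them co-primary, and no rule says which part governs.

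The choice is more than a label, because the two analyses can disagree. They use different models, alpha levels, dropout rules and analysis sets. If one is significant and the other is not, the trial is either a success or, at best, a relative success under 6.I.2, while a reader holding Aim 1 would reach the opposite conclusion. A confirmatory result needs one primary outcome fixed beforehand that can be read in only one way.

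**Working it through.** **1. The two assignments side by side**

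| | Section 3 (Aims 1 and 2) | Sections 6.I.2 and 6.I.6 |
|---|---|---|
| Primary | Drinks per week | PSNHDD |
| PSNHDD | Secondary (Aim 2) | Primary, alpha .05, defines success |
| Drinks per week | Primary (Aim 1) | Secondary, Bonferroni-corrected |

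The analyses attached to each outcome in 6.I.2 are:

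- PSNHDD: logistic regression, intention to treat, and "dropouts will be considered as having relapsed to heavy drinking".
- Drinks per week: a mixed model with group, week and their interaction. Dropouts contribute data until they leave. The set is called intention to treat but is limited to subjects who took some medication and gave at least one week of drinking data.

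**2. Which outcome the primary power figure belongs to**

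Inputs: 12 zonisamide and 7 placebo pilot subjects without relapse (6.I.6); pilot N = 40 (section 3); 80 per arm (6.D.2). Assumed: 20 per pilot arm and a two-sided test. The proportions are then 12/20 = 0.60 and 7/20 = 0.35, with mean 0.475.

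- Standard error under the null: sqrt(2 × 0.475 × 0.525 / 80) = 0.0790.
- Standard error under the alternative: sqrt((0.60 × 0.40 + 0.35 × 0.65) / 80) = 0.0764.
- Power: Phi((0.25 − 1.96 × 0.0790) / 0.0764) = Phi(1.246) = 0.894.

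This reproduces the stated figure of more than 89%, so that figure was built for PSNHDD at .05. It depends on the assumed pilot split: 19 zonisamide and 21 placebo gives 0.971, and 21 and 19 gives 0.734. The same formula gives 0.816 at 64 per arm, where 6.I.6 states about 76%. A continuity correction gives 0.764 there but 0.861 at 80, so one method does not yield both stated figures. The contradiction does not depend on this.

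**3. Familywise error if the label were chosen after seeing the data**

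Two null outcomes, each tested two-sided at .05, with error 1 − P(|Z1| < 1.96 and |Z2| < 1.96). The correlations between test statistics are assumed; the documents give none.

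- Correlation 0: 1 − 0.95² = 9.75%.
- Correlation 0.5: 9.1%.
- Correlation 0.8: 7.8%.
- Correlation 0.9: 7.0%.

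**4. What each choice means for power**

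- PSNHDD primary: 0.894, as above. If it moved to the Bonferroni family, the same formula gives 0.830, 0.729 or 0.645 for 2, 5 or 10 tests. The number of tests is assumed, because the plan does not state it.
- Drinks per week primary: the only stated power is 0.98, for a difference in slopes over 12 weekly measures. A slope-only check uses the 6.I.6 difference 2.2 − 1.4 = 0.8 and variance 0.9: Phi(0.8 / sqrt(2 × 0.9 / 80) − 1.96) = Phi(3.37) = 0.9996. That is an upper bound, since it ignores week-to-week residual variance, which is not given. Neither figure is for a contrast over the eight target-dose weeks on which 6.I.2 focuses.

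**5. Two definitions that matter under either choice**

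- Heavy drinking day: 6.C uses at least 5 drinks for men and at least 4 for women; 6.I.2 prints more than 5 and more than 4 for all analyses. A day of exactly 5 (men) or 4 (women) counts under one and not the other.
- Window: 6.I.2 asks for eight weeks at target dose after a six-week grace period. Section 6.A and Table 1 have seven titration weeks, although the text above Table 1 speaks of a six-week titration phase. Section 6.I.4 uses the final eight treatment weeks and calls this consistent with Aim 1.

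**The case against.** The strongest reply is that the statistical section governs and is consistent: 6.I.2 allocates alpha, defines success and says how to regard a positive secondary result. Section 6.I.6 agrees, and 6.I.7 also names PSNHDD apart from the secondary outcomes. On that view the aims are simply out of step. Much of this stands. The operative rules point one way, and different models and dropout rules for a binary and a repeated outcome are normal. But no precedence rule is written, and a stated Primary Aim is where readers look for the primary outcome.

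Four stronger readings are tempting but unsupported:

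- **That the plan as written inflates type I error.** It does not. Section 6.I.2 gives .05 to one outcome and corrects the rest.
- **That the primary outcome was switched.** Section 6.I.6 refers to a previously planned sample size, which may hint at an earlier design, but the text shows neither whether nor in which direction the outcome changed.
- **That 6.A and Table 1 define a rival nine-week analysis window, or that the grace period puts the window at weeks 7 to 14.** Section 6.A and Table 1 give a dosing schedule, not an analysis window. Table 1 has week 7 at 400 mg, so a window starting then would break the target-dose condition in 6.I.2. What remains is a six-week grace period set against seven titration weeks.
- **That two heavy-drinking-day thresholds are established.** The strict inequality in 6.I.2 may be an at-least sign lost in the PDF text, so the source must be checked first.

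**Conclusion.** The contradiction is real and rests on the text alone: Section 3 and Section 6.I assign the primary and secondary ranks in opposite ways, and nothing reconciles them. The documents lean towards PSNHDD in their operative rules but do not settle which outcome was intended.

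The statistical harm is conditional. With the label fixed beforehand, error stays at the planned level; the 7% to 10% range applies only to a choice made after seeing the data. The power figures rest on the assumed equal pilot split, and those for a Bonferroni-tested PSNHDD also on assumed test counts. The definition and window points are smaller. They need settling because a single heavy drinking day inside the window decides a subject's PSNHDD result.

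**What to change.** Before unblinding, the investigators confirm one primary outcome and make Aim 1 (outcome and hypothesis), Aim 2, 6.I.2 and 6.I.6 agree.

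- **If PSNHDD:** reword Aim 1 and its hypothesis to PSNHDD and move drinks per week to Aim 2. Model, alpha and power are already in 6.I.2 and 6.I.6. Cost: wording only.
- **If drinks per week:** assign the .05 to one named contrast of the 6.I.2 mixed model over the eight target-dose weeks, move PSNHDD into the Bonferroni family, and restate power for that contrast. Cost: wording plus one new power simulation. Whether N = 160 suffices is unknown until it is run.
- **Under either option:** check the source PDF for the inequality sign and use one heavy-drinking-day definition in 6.C and 6.I.2. Reconcile the six-week and seven-week statements, and give the eight-week window as numbered study weeks in 6.I.2 and 6.I.4. These are text edits on data already collected by timeline follow-back. They can change who counts as a success, so they must also be settled before unblinding.

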Medication administration and medication-related adverse events. In addition to regular monitoring of vital signs, subjective reports of side effects will be monitored weekly using a list of adverse effects that have previously been reported for ZNS. A commonly used form (SAFTEE) for assessing and tracking side effects, their severity (on a scale of 1-5), and resolution, will be implemented.

Measures of treatment received. At each treatment visit, patients will be asked to return the unused portion of study medication. Staff will record the number of contact hours patients have been exposed to any treatment outside of the study that is related to their drinking and any self-help group attendance.

(c). Areas Assessed At Intake And At Treatment Endpoint:

Alcohol-related problems. The Short Index of Problems (SIP), which measures alcohol-related problems in five domains, will be used to assess change in such problems reported by patients in this trial (80). The SIP has good internal consistency, good concurrent validity, and adequate stability. The RAND 36-Item Health Survey, a 36-item self-report measure of life functioning in various domains, will be completed at study baseline, endpoint, and follow-ups. The Quality of life enjoyment and satisfaction survey (Q-LES-Q) will be used to assess quality of life in subjects.

(d). Areas Assessed Only At Treatment Endpoint:

Endpoint rating form. This is to be completed by the research assistant when the patient leaves treatment, indicating the patient's level of functioning at termination, and to chronicle as specifically as possible the reasons for termination (i.e., dropout, symptomatic failure, failure to comply with treatment), other circumstances behind the decision to terminate treatment, and who made the decision to terminate the treatment (patient, therapist, physician).

Brief 30 day assessment of Alcohol Dependence Symptoms. Subjects will be asked about AD symptoms for the last 30 days of treatment to assess for remission from the diagnosis.

Assessment of tolerability, efficacy, and masking questionnaire. This is a five-page questionnaire that measures the subject's subjective evaluation of the efficacy and tolerability of the medication, provides an opportunity for feedback on the study, and evaluates the success of the medication blinding procedure.

(e). Areas Assessed daily:

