We will use a mixed models approach to examine **secondary outcome measures (Specific Aim 2)** for a statistically significant difference in; drinks per week, and heavy drinking days per week, the outcomes used in the pilot study. The model will include fixed effects for medication group, week, and the interaction between medication and week, also controlling for pre-treatment drinking behavior data, and using a random effect for intercept. We will incorporate a grace period corresponding to the time it takes to titrate the medication to target dose into the models, and we will focus the primary analysis on the 8 weeks of treatment at the target dose. Aggregate outcome measures such as the percentage of heavy drinking days, which can be examined using several different methods, will be considered. A statistically significant difference on any of the secondary measures of both heavy drinking and drinking, with clinically significant effect sizes, will be considered a relative success for the medication. Additional secondary outcome measures will include changes in GGT level, measures of alcohol urge or craving to use (AUQ), measures of depression and anxiety, measures of physical health and quality of life (Q-LES-Q, the and the RAND-36) and level of alcohol-related problems (as measured on the SIP). These can also be performed with the mixed models approach. Statistical models evaluating time to relapse, drinking trajectories, percentage of abstinent days, drinks per drinking day, and total abstinence rates will be considered. **We will use the Bonferroni correction for the secondary outcomes and additional comparisons to guard against chance findings.**

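### Non-drinking secondary outcomes in 6.I.2 are not adjusted for their own baseline, and the response used for SIP, RAND-36 and Q-LES-Q is left unstated

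*Combined protocol and SAP*

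**What the plan says.** The Aim 2 hypothesis in section 3 is that "ZNS will demonstrate significantly greater improvements than the placebo on these measures by the treatment endpoint as well as at follow-up". Besides drinking outcomes, that aim names "the urge to drink (craving), biomarkers of alcohol intake, clinical global impression, medication tolerability, and other patient-centered outcomes". Mood, quality of life and alcohol-related problems are not named there. They enter in 6.I.2, so 6.I.2 is the text to amend.

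Section 6.I.2 writes the secondary model for drinks per week and heavy drinking days per week. It has "fixed effects for medication group, week, and the interaction between medication and week, also controlling for pre-treatment drinking behavior data", "using a random effect for intercept", and a window described as "we will focus the primary analysis on the 8 weeks of treatment at the target dose". The section then lists change in GGT, AUQ, depression and anxiety measures, Q-LES-Q, RAND-36 and SIP, and says of them: "These can also be performed with the mixed models approach". For the three-month follow-up it again names only drinking data (pre-treatment and within-treatment) as covariates.

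The measurement schedule in the text is:

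- AUQ and BDI at each treatment visit, STAI weekly (6.F.2(b)).
- GGT at screening, then after week 4, at week 8 and at week 16 (6.D.1, 6.F.1).
- SIP, RAND-36 and Q-LES-Q under the heading "Areas Assessed At Intake And At Treatment Endpoint" (6.F.2(c)). The same paragraph adds follow-ups for RAND-36, and 6.D.7 lists quality of life at three months.

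**The concern.** Improvement is measured from where the subject started. Pre-treatment drinking is the natural baseline for drinking outcomes. It is not the baseline of a craving, depression, quality-of-life or alcohol-problems score. Those baselines are collected, but the plan gives them no role in the analysis.

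Two things are at stake. First, precision: a weakly related covariate removes little residual variance, on outcomes that also face a Bonferroni correction. A chance difference between arms on the outcome's own baseline also stays in the estimate. Second, pre-specification: for the three scales with one on-treatment value, the model cannot be fitted as described unless the analyst decides what goes into the response. The possible choices have different power and could give different p-values.

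**Working it through.** **Inputs.** From the documents: 80 per arm (6.D.2), the model terms (6.I.2) and the visit schedule (6.F.1, 6.F.2). Not in the documents, so assumed: true difference 0.4 SD, two-sided alpha .05 before Bonferroni, one endpoint value per subject, correlation of baseline drinking with the outcome r = 0.2 (range 0 to 0.3), and correlation of own baseline with the outcome rho = 0.3 to 0.7. Section 6.I.6 gives power only for PSNHDD, drinks per week and heavy drinking days per week, so there is no stated figure to reproduce.

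**1. Can the model be fitted?** The fixed effects are intercept, group, week and group × week.

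| Values in the response | Rank of design | Result |
|---|---|---|
| Week 16 only | 2 of 4 | Week is 16 × intercept and group × week is 16 × group, so neither is estimable. Only the sum of random-intercept and residual variance is identified. A trial fit failed with a singular matrix. |
| Baseline and week 16 | 4 of 4 | Fits. Group × week is the difference in change from own baseline. |
| Week 16 and one later follow-up | 4 of 4 | Estimable. |
| GGT at weeks 4, 8 and 16 | 4 of 4 | Estimable. |

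Weekly AUQ, BDI and STAI have no fitting problem either. Estimability is therefore a question for SIP, RAND-36 and Q-LES-Q only.

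**2. Precision of an endpoint contrast.** Adjusting for a covariate with correlation c leaves residual variance 1 − c². The effective difference is 0.4/√(1 − c²), put into a two-sample t-test with 80 per arm.

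| Covariate | c | 1 − c² | Effective difference | Power |
|---|---|---|---|---|
| None | 0 | 1.00 | 0.400 | 0.71 |
| Baseline drinking | 0.2 | 0.96 | 0.408 | 0.73 |
| Own baseline | 0.3 | 0.91 | 0.419 | 0.75 |
| Own baseline | 0.5 | 0.75 | 0.462 | 0.83 |
| Own baseline | 0.7 | 0.51 | 0.560 | 0.94 |

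Against the drinking covariate at r = 0.2, the variance ratios are 0.91/0.96 = 0.95, 0.75/0.96 = 0.78 and 0.51/0.96 = 0.53. If own baseline and drinking both correlate 0.3, the ratio is 0.91/0.91 = 1 and nothing is gained.

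The plan does not state the number of Bonferroni tests. If the nine continuous outcomes named in 6.I.2 are counted (an assumption; alpha .05/9 = .0056), power is 0.41 with the drinking covariate, against about 0.55 and 0.77 with own baseline at rho 0.5 and 0.7.

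**3. Chance imbalance.** The 95% range for a baseline difference between arms is ±1.96 × √(2/80) = ±0.31 SD. With no adjustment, an imbalance of that size moves the endpoint contrast by about rho × 0.31: 0.09, 0.16 and 0.22 SD at rho = 0.3, 0.5 and 0.7. A drinking covariate removes this only so far as drinking tracks that outcome's baseline.

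**4. Baseline in the response.** An unconstrained two-point model compares change scores, with variance 2(1 − rho) against 1 − rho² for ANCOVA.

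| rho | Change-score variance | Power | ANCOVA variance | Power |
|---|---|---|---|---|
| 0.3 | 1.40 | 0.57 | 0.91 | 0.75 |
| 0.5 | 1.00 | 0.71 | 0.75 | 0.83 |
| 0.7 | 0.60 | 0.90 | 0.51 | 0.94 |

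Up to rho = 0.5 the change-score version does no better than an unadjusted endpoint comparison (0.71).

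**5. Slopes for weekly outcomes.** In a balanced random-intercept model, a baseline main effect leaves the group × week term unchanged. In a simulation of 80 per arm over 8 weeks, with a baseline correlated 0.6 with the subject intercept, the estimate was −0.0553 (SE 0.0175) with and without the covariate. The gain in step 2 applies to the group-level or endpoint contrast, not to the slope.

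**The case against.** The strongest reply is that 6.I.2 writes the drinking covariate for drinking outcomes, and its later sentence about the other measures only names a class of method. On that view the plan is under-specified, and no wrong covariate has been chosen. This is fair as far as it goes. Still, no other specification is offered, and the follow-up paragraph repeats the drinking-only covariates. The plan's intention to look for baseline differences between groups does not commit it to adjusting for them.

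A reader might infer that SIP, RAND-36 and Q-LES-Q cannot be analysed at all. The documents do not support that. 6.I.2 speaks of change in GGT and describes a repeated-measures approach that handles baseline and follow-up times, so baseline may be meant to enter the response, and then the model fits. RAND-36 and quality of life are also collected at follow-up. Table 2 shows three post-baseline marks for each of the three scales, but its columns do not align reliably with the text (PEth falls at weeks 7, 11 and 16, where 6.F.1 gives 8, 12 and 16). I have followed the text. If week 15 were a real visit for these scales, there would be two on-treatment values.

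A reader might also infer bias. Omitting own baseline does not bias a randomised comparison on average.

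Three further points stand. The correlations and effect size are assumptions, and r = 0.2 may be too low for GGT and SIP, which relate closely to drinking. The slope test for weekly outcomes gains nothing. Week-16 ANCOVA drops subjects without a week-16 value, whereas the plan intends to use all available data.

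**Conclusion.** The point holds as a loss of precision and a gap in pre-specification. The plan's only stated baseline covariate for these outcomes is pre-treatment drinking, and own-baseline adjustment appears nowhere, although every baseline is collected. On the assumptions given, power for an endpoint contrast rises from about 73% to between 75% and 94%, depending on the own-baseline correlation, and by nothing if the two correlations are equal. These figures are illustrative, because the documents supply neither the correlations nor an effect size for these outcomes.

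The fitting problem is conditional. It arises only for SIP, RAND-36 and Q-LES-Q, and only with baseline kept as a covariate and the response limited to on-treatment values. Putting baseline into an unconstrained two-point response removes the problem but gives a less efficient analysis than ANCOVA. The documents do not support a reading that Aim 2's secondary results would be biased or unobtainable.

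**What to change.** In 6.I.2:

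- State that each non-drinking secondary outcome is adjusted for its own baseline value, with pre-treatment drinking optional in addition. Make the same change in the follow-up paragraph.
- Name the tested contrast: the group difference over the target-dose weeks, or at week 16.
- For SIP, RAND-36 and Q-LES-Q, specify either ANCOVA at week 16 on the baseline score, or a model with baseline in the response and baseline means constrained equal across arms. The second option also keeps subjects who lack a week-16 value, in line with the plan's use of all available data.
- A log transformation of GGT is optional.

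The cost is a few sentences of wording. No new data, visits or subjects are needed, but the change should be made before unblinding.
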